10.6. Exploratory Analyses

Each component of the study endpoint (all-cause death, liver transplant, and hospitalization for hepatic decompensation) will be assessed separately. For the outcome of death, the analysis will proceed using the same approach as for the primary effect size estimation. For the outcome of liver transplant, death will be treated as a competing event. Here, follow-up will end at the earliest of the end of follow-up, liver transplant, death, or censoring. The analysis will proceed as previously described, but instead of a Cox proportional hazards model, a Fine-Gray proportional subdistribution hazards model will be used (Fine 1999). Similarly, for the outcome of hospitalization for hepatic decompensation, death and liver transplant will be treated as competing events.

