The exploratory objectives are to estimate the effect of OCA treatment versus non-OCA treatment on each component of the composite endpoint (all-cause death, liver transplant, or hepatic decompensation). The exploratory analysis outcomes will be assessed with the subdistribution hazard ratio comparing the hazard of the first event of each element of the composite endpoint, separately, among the OCA-treated patients and standardized morbidity ratio-weighted non–OCA-treated PBC patient indices. For the endpoint of liver transplant, death will be treated as a competing event. For the endpoint of hepatic decompensation, death and liver transplant will be treated as competing events. The subdistribution hazard ratio will be estimated using a Fine-Gray proportional subdistribution hazards model. The nonparametric bootstrap will be used to estimate the standard error of the estimates, which will then be used to calculate 95% CI for the hazard ratio and perform a test of the hypothesis that the hazard ratio is equal to the null value of 1.

Sample Size Justification:

Using the expected sample size in the 2 populations, the Sponsor computed power to detect treatment effects (relative hazards) of varying sizes, estimated using Cox proportional hazards regression. Computations are based on the formulae of Schoenfeld 1983. To account for confounding control due to the application of IP weights, the Sponsor inflated the variance from the Schoenfeld formula using factors derived by Shook-Sa 2020. It was conservatively assumed just one control observation per patient. In the Komodo Health data, a preliminary investigation found that approximately 395 patients who meet entry criteria initiate OCA and that 5916 patients will contribute at least one record to the control group (UDCA nonresponders). In the Global PBC registry, the Sponsor expects to have 344 patients meeting entry criteria who initiate OCA, and 2200 who contribute at least one observation to the control group. Power in both cohorts was computed for relative hazards ranging from 0.5 to 0.9 with an alpha level of 0.05. The Sponsor considered baseline event rates during follow-up from 5% to 15% and variance inflation corresponding to mild confounding (VIF=1.05), moderate confounding (VIF=1.5), and strong confounding (VIF=2.0). In each study, power was plotted under these assumptions against a reference line of 80% power under moderate confounding (VIF=1.5).

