definition or the definition of OCA initiation, as well as all other inclusion criteria, they will contribute an index to the study. Therefore, patients may contribute multiple control indices, and may contribute control indices before OCA initiation, but can contribute only one OCA initiation index. The non–OCA-treated patient indices will be weighted to have the same baseline covariate distribution as the OCA-treated patients at the time of OCA initiation, thus allowing for the estimation of the effect of treatment in the treated. Patients must have 12 months of data preceding the index date (ie, the pre-index period) to establish the medical history and OCA eligibility and for the standardized morbidity ratio-weighting. Follow-up of patients will be until the first occurrence of the composite endpoint. Patients will be censored at drop out/disenrollment from the database, discontinuation of OCA (+90 days), initiation of fenofibrate or bezafibrate, initiation of OCA (for the non–OCA-treated patient indices), unapproved OCA dose (>10 mg QD) for those treated with OCA, or the end of the study period (31 Dec 2021); whichever comes first.

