Because treatment non-adherence and loss to follow-up may not occur completely at random, those who remain uncensored may differ from the overall study population on key prognostic factors. To address these differences, the Sponsor will include baseline covariates in the Cox model that are potential predictors of both the study outcomes and censoring.

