10.3. Hypotheses

10.3.1. Primary Hypothesis

These studies are intended to assess whether there is a difference between patients treated with OCA and comparable OCA-eligible patients who are not treated with OCA in the time from index to the first occurrence of all-cause death, liver transplant, or hospitalization for hepatic decompensation.

Two-sided hypotheses are expressed in terms of:

- The null hypotheses (H₀) that the 2 hazard functions are the same, as determined by a hazard ratio (HR) equal to 1; that is, at every timepoint, the instantaneous event rates are the same for the OCA and control populations.
- The alternative hypothesis (H₁) that the 2 hazard rates are not the same ($HR \neq 1$).

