10.4. Determination of Sample Size

Using the sample size in the 2 populations (Section 6.2), the Sponsor computed power to detect treatment effects (relative hazards) of varying sizes, estimated using Cox proportional hazards regression. Computations are based on the formulae of Schoenfeld 1983. To account for confounding control due to the application of IP weights, the Sponsor inflated the variance from the Schoenfeld formula using factors derived by Shook-Sa 2020. It was conservatively assumed just one control observation per patient. In the Komodo Health data, a preliminary investigation found that approximately 395 patients who meet entry criteria will initiate OCA and that 5916 patients will contribute at least one record to the control group (UDCA nonresponders). In the Global PBC registry, the Sponsor expects to have 344 patients meeting entry criteria who initiate OCA, and 2200 who contribute at least one observation to the control group. Power in both cohorts was computed for relative hazards ranging from 0.5 to 0.9 with an alpha level of 0.05. The Sponsor considered baseline event rates during follow-up from 5% to 15% and variance inflation corresponding to mild confounding (VIF=1.05), moderate confounding (VIF=1.5), and strong confounding (VIF=2.0). In each study, power was plotted under these assumptions against a reference line of 80% power under moderate confounding (VIF=1.5) (Figure 2).

Under mild confounding, both studies will be well-powered to detect an HR of 0.5. For moderate confounding, the Komodo Health study will be adequately powered to detect HR of 0.5 for event rates >6%. The Global PBC registry will be adequately powered to detect event rates >8%. Under strong confounding, the Komodo Health study will be adequately powered to detect

HR of 0.5 for event rates >9%. The Global PBC registry will be adequately powered to detect event rates >11%. Power decreases for more moderate HRs. None of the studies under even the most favorable assumptions will be able to detect HRs of 0.9. The Sponsor notes that the assumptions made here are conservative; in particular, it is expected that many more than one control observation and that the addition of lab data from LabCorp (as noted in Section 6.2) will substantially increase the size of both groups in the Komodo Health study.

Figure 2: Power estimates by Hazard Ratio by Level of Confounding for Komodo Health (A) and Global PBC Registry (B).

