10.7. Handling of Dropouts or Missing Data

Patients who disenroll from the covered health plans in Komodo Health or from the Global PBC registry are right-censored at time of disenrollment.

Dropout / disenrollment will be assumed to be uninformative conditional on the included baseline covariates in the Cox model (see Section 10.2). Missing baseline data will be assumed missing completely at random, and a complete case analysis (listwise deletion) will be conducted. During the conduct of the studies, the CRC may recommend refining the missing data strategy to better address any observed pattern of missing data.

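### For the exploratory transplant and decompensation components, the Fine-Gray ratio needs a stated by-arm censoring distribution and a cause-specific hazard ratio beside it

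*Combined protocol and SAP*

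**What the plan says.** The Synopsis (Exploratory Analysis) states the aim as estimating the effect of OCA on each component of the composite. It adds: "The subdistribution hazard ratio will be estimated using a Fine-Gray proportional subdistribution hazards model". Section 10.6 analyses death with the weighted Cox approach of the primary analysis. For transplant (death competing) and decompensation (death and transplant competing) it keeps the earlier method, except that "instead of a Cox proportional hazards model, a Fine-Gray proportional subdistribution hazards model will be used".

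The earlier method deals with non-random censoring through the outcome regression. In Section 10.2, "the Sponsor will include baseline covariates in the Cox model that are potential predictors of both the study outcomes and censoring". In Section 10.7, "Dropout / disenrollment will be assumed to be uninformative conditional on the included baseline covariates in the Cox model".

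Section 6.1 lists the censoring events, among them "discontinuation of OCA (+90 days), initiation of fenofibrate or bezafibrate". Some rules apply to one arm only. OCA indices stop at discontinuation plus 90 days or at a dose above 10 mg once daily, and control indices stop at OCA initiation.

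No section says how the censoring distribution inside Fine-Gray is estimated. Section 10.5 repeats all estimation in each bootstrap replicate, but names only the treatment model, the weights and the Cox fit. No cause-specific hazard ratio is planned for transplant or decompensation. In Appendix B, Table 31 and Figure 4 cover only the composite.

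**The concern.** In a Cox model with treatment as a covariate, censoring that depends only on arm does no harm, because censored records simply leave the risk set. Fine-Gray differs. A patient who has had the competing event stays in the risk set with weight G(t)/G(s), where s is the time of that event and G is the censoring distribution. Covariates in the regression do not repair G. If one G serves both arms while the arms are censored at different speeds, the two risk sets are distorted by different amounts.

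A second issue is independent of censoring. The subdistribution hazard ratio (sHR) depends on the component hazard and on the competing hazard. If more OCA patients die first, fewer remain to decompensate or be transplanted, and the sHR falls although OCA does nothing to the component. On its own, then, the sHR cannot answer the stated question about each component.

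**Working it through.** **1. The plan's own figures.** The plan gives none for Fine-Gray. Its power statement for the composite (Section 10.4: "relative hazards ranging from 0.5 to 0.9 with an alpha level of 0.05"; Section 10.3.1: "Two-sided hypotheses are expressed in terms of") can be reproduced and supplies the scale of the standard errors. For HR 0.5 and 80% power, events D must satisfy D/VIF = (1.96 + 0.842)² / [(ln 0.5)² p(1−p)], with p the OCA share. D is the control rate times (controls + half the OCA patients).

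- Komodo: p = 395/6311 = 0.0626 and p(1−p) = 0.0587, so D/VIF ≈ 278. The divisor is 5916 + 197.5 = 6113.5. Crossing rates are 6.8% (VIF 1.5) and 9.1% (VIF 2.0).
- Registry: p = 344/2544 = 0.1352 and p(1−p) = 0.1169, so D/VIF ≈ 140. The divisor is 2200 + 172 = 2372. Crossing rates are 8.8% and 11.8%.

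Truncated to whole percent, these are the stated 6, 9, 8 and 11.

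**2. Mechanism.** With constant hazards λ1 (component) and λ2 (competing), censoring rate c and uniform staggered entry over 5.6 years, the proportion at risk is Y(t) = (1 − t/5.6)·exp{−(λ1+λ2+c)t}. The Fine-Gray risk set is R(t) = Y(t) + ∫₀ᵗ Y(s)·λ2·G(t)/G(s) ds. If each arm uses its own G, c cancels from Y/R and the null sHR is exactly 1.

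A hand check uses the OCA arm at t = 2 years, λ1 = λ2 = 0.05 and c = 0.40. The entry factor cancels.

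- Still at risk: e^(−1.0) = 0.368.
- Retained after a competing event, own-arm G: 0.05·e^(−0.8)·(1−e^(−0.2))/0.1 = 0.041.
- Retained, G taken from controls (c = 0.08), the limit of a pooled G with many controls: 0.05·e^(−0.16)·(1−e^(−0.84))/0.42 = 0.058.
- Ratio of risk sets: 0.409/0.426 = 0.96.

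At two years the OCA subdistribution hazard is understated by about 4%. Events are concentrated earlier, so the average over follow-up is smaller.

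**3. Size over follow-up.** I solved the Fine-Gray score equation for the same model. The hazards and censoring rates are assumptions, not figures from the documents. Control censoring is 8%/yr and the pooled G uses the Komodo ratio 5916/395 ≈ 15. Changing λ1 between 2% and 5%/yr moves results by about 0.001.

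| Competing hazard | OCA censoring | Null, pooled G | Null, G by arm | OCA death hazard ×2, pooled G | OCA death hazard ×2, G by arm |
|---|---|---|---|---|---|
| 2%/yr | 25%/yr | 0.992 | 1.000 | 0.956 | 0.970 |
| 2%/yr | 40%/yr | 0.986 | 1.000 | 0.947 | 0.973 |
| 5%/yr | 25%/yr | 0.983 | 1.000 | 0.901 | 0.929 |
| 5%/yr | 40%/yr | 0.969 | 1.000 | 0.884 | 0.936 |

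The cause-specific HR for the component is 1.00 in every row. The doubling is applied to the whole competing hazard, treated as death. The registry ratio (2200/344 ≈ 6.4) changes the pooled figures by at most 0.002. Equal censoring gives 1.000. Faster control censoring gave 1.003 to 1.028.

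**4. Against the plan's event rates.** With both hazards at 2, 3 or 5%/yr, about 9%, 13% or 21% of controls have an event. Section 10.4 considers 5–15%, so the rows with both hazards at 5%/yr lie beyond it. A second parameterisation fixed competing incidence at 5–10% and varied the censoring. With OCA censored faster and G pooled, it gave a null sHR of 0.977–0.998 with staggered entry and 0.953–0.997 without. At 15% the worst values were 0.967 and 0.932. With death HR 2, equal censoring, staggered entry and control death incidence of 5, 10 or 15%, the sHR was 0.985, 0.969 or 0.954.

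**5. Against precision.** SE(log sHR) ≈ √[VIF/(p(1−p)D)].

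- Komodo, 10% component rate, VIF 1.05: D = 631 and SE = 0.17.
- Registry, 5% component rate, VIF 1.5: D = 127 and SE = 0.32.

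Since ln 0.97 = −0.030, the drift is at most about 0.18 SE. Two-sided type I error for a null sHR of 0.97–0.99 is 0.050–0.054.

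**The case against.** Three stronger readings are tempting, and the documents support none of them.

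- **The component ratios will be biased in favour of OCA.** This needs a pooled G and faster OCA censoring. The plan states neither and gives no discontinuation or switching rates. Faster OCA censoring is plausible. Even if every initiator had first been a control, switchers would be at most 395/5916 = 6.7% of Komodo controls and 344/2200 = 15.6% in the registry, and Section 4.6.1 reports pruritus in 80% of OCA-treated trial subjects. But fibrate starts censor both arms at unknown rates, and SMR weighting raises the weighted share of switchers. Direction stays conditional.
- **A death harm would be hidden.** It would not. Death has its own weighted Cox analysis and is part of the composite, so a doubled death hazard would appear beside the component results.
- **The sHR is wrong.** A lower sHR correctly reflects a lower cumulative incidence. Choosing between it and the cause-specific ratio is a choice of estimand. The death-mixing effect is unrelated to the censoring remedy and persists with G by arm.

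It is also fair to say that a drift of 1–3% in an exploratory ratio would change no conclusion. What stands is that G is unspecified, that the carried-over remedy does not reach it, and that no planned output tells a reader whether a component ratio below 1 reflects fewer decompensations among those still at risk or more deaths beforehand.

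**Conclusion.** The point holds as a cheap improvement of low severity. The text extends a censoring argument made for Cox to a model where it does not cover the weights. Under the assumed hazards and censoring rates, a pooled G with faster OCA censoring puts the null sHR at about 0.97–0.99. That is well below one standard error, with essentially no effect on type I error. Separately, a doubled OCA death hazard with no component effect gives about 0.93–0.97 with G by arm, nearer the upper end or above at the event rates of Section 10.4.

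These figures rest on constant hazards and on censoring that depends only on arm. Discontinuation related to prognosis was not modelled; it would bias the Cox analyses too. Section 10.8 repeats the analysis by cirrhosis status. Both effects grow with the competing-event rate, so they would be larger in any subgroup where that rate is higher.

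**What to change.** In Section 10.6 and the Synopsis:

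1. For transplant and decompensation, report the cause-specific hazard ratio from the same SMR-weighted, covariate-adjusted Cox model beside the Fine-Gray ratio, ending follow-up at the competing events already named. The covariate argument of Sections 10.2 and 10.7 then applies as written.
2. State that the Fine-Gray censoring distribution is estimated separately by treatment group and refitted in each bootstrap replicate, and add it to the steps named in Section 10.5.
3. Add to Appendix B the weighted cumulative incidence of each component and of its competing events, by arm.

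The cost is SAP wording, one extra Cox fit per component inside the existing bootstrap, and two ratios per exploratory component instead of one. The primary analysis is unchanged.

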10.7. Handling of Dropouts or Missing Data

Patients who disenroll from the covered health plans in Komodo Health or from the Global PBC registry are right-censored at time of disenrollment.

Dropout / disenrollment will be assumed to be uninformative conditional on the included baseline covariates in the Cox model (see Section 10.2). Missing baseline data will be assumed missing completely at random, and a complete case analysis (listwise deletion) will be conducted. During the conduct of the studies, the CRC may recommend refining the missing data strategy to better address any observed pattern of missing data.

10.8. Subgroup Analyses

The entire analysis will be repeated separately by patient race (Komodo Health only), age (categorical), sex, region, absence/presence of cirrhosis, and pre-/post-COVID. Because race is not completely captured in Komodo Health, these analyses will only include those with non-missing values for race.

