4. INTRODUCTION

4.1. Overview of Disease State and OCA

Primary biliary cholangitis, (PBC) is a serious, life-threatening, cholestatic liver disease of unknown etiology that, without treatment, frequently progresses to hepatic fibrosis and eventual cirrhosis or hepatic decompensation and necessitates liver transplantation or results in death. PBC is a rare disease with a reported prevalence in the United States (US) of 40/100,000 (Kim 2000). PBC disproportionately affects women (with a female to male ratio of approximately 10:1) and is typically diagnosed in patients aged 40 to 60 years.

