6.2. Number of Patients

The Komodo Health database contains administrative claims from >350 US payers, tokenized to allow for patient tracking across payers. Komodo Health claims will be linked through Datavant tokenization to Quest Diagnostics and LabCorp laboratory data, the US National Death Index (NDI), and the Organ Transplant Network (OPTN) transplant registry for additional information and outcome verification. The database contains >100,000 patients with a PBC diagnostic code. The Global PBC registry includes >5,000 patients with PBC recruited from 17 liver centers across 8 countries in Europe and North America. It utilizes the CASTOR trial platform for

electronic case report form (eCRF) collection of medical history, clinical events, and laboratory and treatment data.

Komodo Health: In the current Komodo Health database, there are 395 patients who meet criteria for the OCA treatment group:

- Meet PBC claims diagnostic criteria (1 inpatient or 2 outpatient claims)
- Initiate OCA treatment
- Have evidence of UDCA failure

There are 5916 who meet criteria for the control group (OCA-eligible but not currently OCA-treated)

- Meet PBC claims diagnostic criteria (1 inpatient or 2 outpatient claims)
- Have at least 270 days of UDCA use before elevated ALP and/or TB inclusive of up to 4 instances of elevation (inadequate response) or ≤90 days UDCA use before elevated ALP and/or TB (intolerant)
- Have evidence of ALP >ULN and/or TB >ULN

The Komodo Health data have not yet been linked to LabCorp laboratory data. It is anticipated that these numbers will approximately double with the availability of LabCorp data.

Global PBC Registry: The Global PBC registry data are currently being refreshed. A previous analysis identified that 344 patients who had initiated OCA. Among the >5000 patients not treated with OCA, it is anticipated that >2200 will meet criteria for UDCA failure and for inclusion in the control group (Corpechot 2008, Kumagi 2010).

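### Subgroup analyses repeat the whole weighted analysis in each subgroup, plan no comparison of effects between subgroups, and have no rule for groups with very few OCA events

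*Combined protocol and SAP*

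**What the plan says.** Section 10.8 is the whole subgroup plan: "The entire analysis will be repeated separately by patient race (Komodo Health only), age (categorical), sex, region, absence/presence of cirrhosis, and pre-/post-COVID". Its only other sentence restricts the race analyses to patients with race recorded. Taken literally, the repeated analysis has three parts:

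- the logistic treatment model with main effects for every covariate, and the SMR weights built from it (Section 10.1.1);
- the weighted Cox model, which also carries baseline covariates (Section 10.2);
- 1000 patient-level bootstrap replicates that redo every step. The standard deviation of the log HR across replicates is the standard error for the CI and the Wald test (Section 10.5).

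The plan gives no treatment-by-subgroup term or contrast, no minimum subgroup size or event count, no age bands and no COVID date. Appendix B has no shell for subgroup results. The one interaction in the plan, in Section 10.2, is between treatment and nested trial, which is a different question. Section 10.1.1 lets the team simplify or penalise the weight model if it fails to converge or leaves imbalance. Nothing comparable covers the Cox model or a bootstrap replicate without OCA events.

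**The concern.** Two things are at stake.

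First, a set of separate HRs and p-values does not show whether the effect of OCA differs between subgroups. Without a contrast, the reader is left to set a significant subgroup beside a non-significant one, which is not a comparison of effects.

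Second, a procedure sized for the full cohort is carried unchanged into groups that may hold only a few OCA events. There the HR rests on one or two patients, and the bootstrap standard error, on which both the CI and the p-value depend, can break down.

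**Working it through.** **The plan's own figures.** Section 10.4 states power for the full cohorts only: "Power in both cohorts was computed for relative hazards ranging from 0.5 to 0.9 with an alpha level of 0.05". Section 10.3.1 makes the test two-sided. Events needed for 80% power are D = (1.96 + 0.842)² × VIF / [p(1 − p)(ln HR)²], where p is the OCA share. At HR 0.5:

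- Komodo, p = 395/6311 = 0.0626: D = 418, or 6.6%, at VIF 1.5 (plan: above 6%); D = 557, or 8.8%, at VIF 2.0 (plan: above 9%).
- Registry, p = 344/2544 = 0.135: D = 210, or 8.2%, at VIF 1.5 (plan: above 8%); D = 279, or 11.0%, at VIF 2.0 (plan: above 11%).

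Three of the four agree closely. Komodo at VIF 1.5 has 76% power at 6%, which does not affect this point. No figure is given for any subgroup.

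**OCA men.** Inputs are "approximately 395 patients who meet entry criteria will initiate OCA and that 5916 patients will contribute at least one record to the control group" for Komodo, "344 patients meeting entry criteria who initiate OCA, and 2200 who contribute at least one observation to the control group" for the registry, and "a female to male ratio of approximately 10:1" from Section 4.1, so men are 1/11. Section 6.2 adds for Komodo: "It is anticipated that these numbers will approximately double with the availability of LabCorp data". OCA men therefore number 395/11 = 35.9 in Komodo, 790/11 = 71.8 if it doubles, and 344/11 = 31.3 in the registry. Expected OCA events are n × [1 − (1 − r)^HR], with r the baseline event rate:

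| | r 5%, HR 0.5 | 5%, HR 1 | 10%, HR 0.5 | 10%, HR 1 | 15%, HR 0.5 | 15%, HR 1 |
|---|---|---|---|---|---|---|
| Komodo, 36 men | 0.9 | 1.8 | 1.8 | 3.6 | 2.8 | 5.4 |
| Komodo doubled, 72 men | 1.8 | 3.6 | 3.7 | 7.2 | 5.6 | 10.8 |
| Registry, 31 men | 0.8 | 1.6 | 1.6 | 3.1 | 2.4 | 4.7 |

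At 10% and HR 0.5, the chance of no OCA event at all is 0.9^(36/2) = 15% in Komodo and 0.9^(31/2) = 19.5% in the registry.

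**Weight model.** Section 10.1.1 lists 11 single-term covariates, plus insurance in five levels (four terms) for Komodo. With sex constant, that leaves 14 terms in Komodo (36/14 = 2.6 OCA men per term) and 10 in the registry (31/10 = 3.1).

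**Bootstrap.** With k OCA events among 36 OCA men, the share of replicates with none is (1 − k/36)^36: 36% for k = 1, 12.8% for k = 2, 4.4% for k = 3 and 0.5% for k = 5. Resampling all 574 men together gives (1 − 2/574)^574 = 13.5% for k = 2, so about 13% either way. In such a replicate the log HR runs to minus infinity. The standard deviation then depends on where the software stops iterating. If those replicates are dropped, the most extreme estimates are removed and the spread is understated.

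**What a contrast could detect.** For Komodo at a 10% control rate, HR 0.5 and VIF 1.5:

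- D = 5916 × 0.10 + 395 × (1 − 0.9^0.5) = 591.6 + 20.3 = 611.9.
- Information I = 611.9 × 0.0626 × 0.9374 / 1.5 = 23.9.
- The log-HR SE in men is √(11/23.9) = 0.68, a CI of the HR divided and multiplied by 3.8, with 17% power (14% in the registry).
- The SE of the log ratio of HRs, men to women, is √(11/23.9 + 1.1/23.9) = 0.71. The ratio detectable with 80% power is exp(2.80 × 0.71) = 7.3.
- Power for a ratio of 2 is 16%.

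The detectable ratio is 16.7 at 5% and 5.1 at 15%. It is 4.1 at 10% if Komodo doubles, and 9.6 at 10% in the registry.

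**The case against.** The strongest reply is that the plan expects models to fail and says what to do. Section 10.1.1 allows a simpler or penalised weight model, and the Clean Room Committee governs such choices. A reader might infer from the small numbers that the subgroup models cannot be fitted. The documents do not support that. In a small simulation of 36 OCA and 538 control men, with assumed covariates, the weight model returned a fit every time, though with near-infinite coefficients in 87% of runs. The HR was not estimable in 15% of runs, those with no OCA event. So the right word is unstable. The fallback covers only the weight model, however, and leaves the zero-event Cox fit and replicate without a rule.

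The counts are derived, not stated. They apply a general-disease sex ratio to OCA initiators, and the lower Komodo figures precede the LabCorp linkage. This stands, and is why ranges are given. The registry has no expected gain of that kind.

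Men are one subgroup, and the result does not carry over to all. Table 2 in Section 12.4.5 implies 14% to 16% compensated cirrhosis among non-decompensated patients, about 54 to 56 OCA patients, in whom event risk may be higher. Nothing here shows that the cirrhosis HR will fail.

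Subgroup effects are not among the stated objectives, and Section 10.8 claims neither consistency nor difference. That stands too, and supports labelling the results descriptive.

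A reader might also infer that the pre-COVID subgroup will be contaminated by COVID-era follow-up. That presumes indices are split by date. Section 10.8 does not say whether indices or follow-up time are split, nor when. The gap is an undefined term.

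**Conclusion.** The point holds in this form: the whole analysis is repeated within each subgroup, effects are never compared between subgroups, and nothing governs groups with very few OCA events. For men the expected count is about 1 to 5 OCA events now, and about 2 to 11 if Komodo doubles. At 2 events about 13% of replicates have no OCA event, so the planned bootstrap SE, CI and Wald p-value cannot be relied on there. This rests on the 10:1 ratio holding among OCA initiators, the sponsor's 5% to 15% event rates, and HRs from 0.5 to 1.

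A reader might take an interaction test as a cure. It asks the right question but is weak: the detectable ratio of HRs by sex is about 7 in Komodo at a 10% rate and VIF 1.5. The gain is an honest interval for the difference, not a verdict on consistency. The primary analysis is unaffected. The change should be made before event data are released under Section 10.1.2.

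**What to change.** In Section 10.8:

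1. For each factor, add the OCA-by-subgroup contrast as a ratio of HRs with a patient-bootstrap 95% CI. Resample patients once per replicate and compute all levels in that replicate, since one patient may supply indices to both levels of a factor such as age or cirrhosis. Show weighted SMDs within each subgroup.
2. Report a subgroup HR, its CI and any contrast using it only where a pre-set minimum number of OCA events is met. Ten is an example and a convention, but it removes the zero-event problem: (1 − 10/36)^36 is below 0.00001. Below the minimum, give event counts only, with no bootstrap Wald p-value.
3. Label the subgroup results descriptive, and state that a non-significant contrast is not evidence of consistency.
4. State whether pre-/post-COVID divides indices or follow-up time, and at what date.

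The cost is SAP wording, a table shell and modest programming. Some subgroups, probably men, will show counts only, and the contrasts that are shown may have wide intervals. Subgroup-specific weights can stay; one pooled model would share covariate effects across subgroups and need not balance the groups within each.
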